7.5 Analysis of Oral Challenge Results

Results of vital signs and focused physical exams (full dose only) after each administration of drug will be summarized in frequencies and percentages for each intervention group (test dose for DOC group; test & full dose for PST group). The type of reactions and severity will be summarized by intervention group and overall.

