6.3.1 One-step Oral Challenge (PST Group)

After confirming the participant is qualified, amoxicillin 250 mg will be administered, and time of administration will be recorded. The subjects will be observed for 60 minutes \pm 10 minutes, after which vital signs, the PE and peak flow will be repeated. Note that each observation time point has a time window of +/- 10 minutes.

If subjects report the presence of difficulty breathing, swelling in lip/mouth/tongue/throat, eye itchiness/tearing, skin hives/itchiness or abdominal pain/nausea/vomiting while they are waiting for final evaluation, study staff will include the reactions with the post-oral challenge vital signs and the focused PE assessment performed after the 60-minute observation period \pm 10 minutes. Standard treatment will be provided, including antihistamines, steroids and/or epinephrine, if indicated and dependent on the specific medical condition that arises.

If vital signs (including peak flow) and focused PE are within reasonable limits after the 60-minute \pm 10 minutes waiting period, the subject will be counseled that they do not have an allergy to PCN (B-lactams). They will be provided with written documentation that they will be encouraged to share with their medical providers, including the STD clinic and their primary care physician (if they have one).

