6.3.2 Two-step Direct Oral Challenge (DOC Group)

Preliminary Dose

After confirming the participant is qualified, amoxicillin 25 mg will be administered, and time of administration will be recorded. The subjects will be observed for 30 minutes \pm 10 minutes, after which vital signs including peak flow will be repeated.

Administration of Full Challenge Dose

If vital signs are within reasonable limits after the 30-minute \pm 10 minutes waiting period, the subject will be given the full challenge dose of 250 mg amoxicillin. The subject will be observed for an additional 30 minutes \pm 10 minutes, after which vital signs, the PE and peak flow will be repeated.

If subjects report the presence of difficulty breathing, swelling in lip/mouth/tongue/throat, eye itchiness/tearing, skin hives/itchiness or abdominal pain/nausea/vomiting while they are waiting for final evaluation, study staff will include the reactions with the post-oral challenge vital signs and the focused PE assessment performed after 30-minute \pm 10 minutes observation period. Standard treatment will be provided, including antihistamines, steroids and/or epinephrine, if indicated and dependent on the specific medical condition that arises.

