6.3.3 Final Outcomes and Determination of Allergy Status

If vital signs (including peak flow) and focused PE are within reasonable limits after the applicable observation periods, subjects will be counseled that they do not have an allergy to PCN (B-lactams). They will be provided with written documentation that they will be encouraged to share with their medical providers, including the STD clinic and their primary care physician (if they have one).

Final outcomes of the oral challenge will be recorded on a CRF as no reaction (negative), reaction (positive) or unevaluable (if the participant leaves the clinic before the applicable observation period is completed). If there is a reaction, after providing standard treatment, study staff will record the type of reaction, severity and how long after the amoxicillin was administered it occurred on the oral challenge testing results CRF.

If reactions to the amoxicillin oral challenge occur, they will be graded and documented using the Toxicity Table (Appendix C).

Rarely, an oral challenge in an individual who skin tests negative can produce an acute reaction (e.g., anaphylaxis) requiring emergency care. Unexpected reactions that place a subject at increased risk will be treated as necessary and reported to the IRB and DMID as required.

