1. INTRODUCTION

This is a multicenter clinical study to screen and enroll eligible individuals coming for care at ambulatory STD clinics and similar venues who self-report a history of PCN or other beta-lactam antibiotic allergy. The study will screen approximately 5,000 men and women to achieve 1,000 evaluable participants from 5 study sites in different geographic areas of the US over a 14-16-month recruitment period.

Two methods of validating PCN allergy will be used:

- **Method 1 – PCN Skin Test (PST) Group:** skin testing of subjects with low-risk history followed by one-step oral challenge of subjects with negative skin tests.
- **Method 2 – Direct Oral Challenge (DOC) Group:** direct two-step oral challenge of subjects with low-risk history.

Each site will perform both allergy validation interventions, Method 1 PST Group and Method 2 DOC Group. The anticipated enrollment at each site will be approximately 200 subjects overall with 100 in each group. Since each intervention has different logistical considerations, sites will enroll subjects in sequential block groups of 25. Sites will be assigned the order of block groups randomly. Each site will plan to enroll 8 block groups, 4 in each allergy validation intervention.

The analysis plan provides additional details regarding the planned statistical analysis of the study protocol (version 2.0, 09March2020). Tables, figures and listings shells will be developed prior to the start of data cleaning and included as an appendix to a future version of the plan.

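### SAP 7.5 misstates the challenge doses by group, so read literally it leaves the DOC group's vital signs and exam after 250 mg untabulated and lists a PST test dose that is never given

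*SAP*

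**What the plan says.** The first sentence of SAP 7.5 covers "Results of vital signs and focused physical exams (full dose only) after each administration of drug", and says that these "will be summarized in frequencies and percentages for each intervention group (test dose for DOC group; test & full dose for PST group". DOC is therefore listed for the test dose alone, and PST for a test dose and a full dose.

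The protocol describes different regimens. For PST, section 6.3.1 says: "After confirming the participant is qualified, amoxicillin 250 mg will be administered". That is the only amoxicillin dose in that group. For DOC, section 6.3.2 starts with 25 mg. If vital signs are acceptable after about 30 minutes, "the subject will be given the full challenge dose of 250 mg amoxicillin", followed by a further observation period, "after which vital signs, the PE and peak flow will be repeated".

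SAP section 1 agrees with the protocol. It describes PST as skin testing "followed by one-step oral challenge of subjects with negative skin tests" and DOC as "direct two-step oral challenge of subjects with low-risk history".

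**The concern.** The parenthesis in SAP 7.5 tells the programmer which group-and-dose combinations to tabulate, and it conflicts with the regimens. Followed as written, it leaves out the DOC group's vital signs after 250 mg. The same sentence restricts the exam to the full dose, so DOC would have no post-dose exam tabulated at all, although protocol 6.3.2 requires one after 250 mg.

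These readings have a use. Protocol 6.3.3 bases the no-allergy message to the subject on them: "If vital signs (including peak flow) and focused PE are within reasonable limits after the applicable observation periods", the subject is told that there is no allergy. DOC subjects also reach 250 mg without a prior skin test, so a reader judging direct challenge would expect to see their findings at that dose.

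**Working it through.** No statistical figure is involved. The check compares the doses given with the doses listed, and then sizes the gap.

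**Terms.** Protocol 2.2.3 uses test dose for the initial 25 mg. Protocol 6.3.2 calls 250 mg the full challenge dose.

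**Comparison.**

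| Group and dose | Given? (protocol 6.3.1, 6.3.2) | Post-dose readings required there | Listed in SAP 7.5? |
|---|---|---|---|
| PST 25 mg | No | None | Yes |
| PST 250 mg | Yes | Vital signs, exam, peak flow at 60 minutes | Yes |
| DOC 25 mg | Yes | Vital signs and peak flow at 30 minutes | Yes |
| DOC 250 mg | Yes | Vital signs, exam, peak flow after a further 30 minutes | No |

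Three sets of readings will exist and SAP 7.5 lists three. Two match, one listed set does not exist (PST 25 mg), and one real set is missing (DOC 250 mg).

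**Could a protocol version difference explain it?** The SAP is written against protocol version 2.0. But its own introduction already has PST as one-step and DOC as two-step, so the conflict lies within the SAP itself.

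**Would swapping the group names repair it?** The line would then read test dose for PST and test plus full dose for DOC. The DOC part would be right. The PST part would name a dose never given and omit the 250 mg that is. The line has to be rewritten.

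**Is the missing set tabulated elsewhere?** SAP 7.2 covers baseline vital signs and exam. SAP 7.4.1 covers elicited reactivity. SAP 7.6 covers skin test results. SAP 7.7 covers adverse events. None tabulates vital signs or exam after 250 mg.

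**Size.** Inputs: 100 planned DOC subjects per site (SAP section 1; protocol 4.1); 5 sites (SAP section 1) or 4 sites (protocol summary).
- 5 × 100 = 500
- 4 × 100 = 400

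With the 5% higher-risk assumption in SAP section 6:
- 500 × 0.95 = 475
- 400 × 0.95 = 380

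All four are upper bounds. Exclusions, refusals and subjects stopped at 25 mg come off them. The documents give no rate of stopping at the first dose. Protocol 2.2.3 cites reaction rates from other direct-challenge studies (in one, 19 of 156, or 12.2%, had any reaction), but those are not rates of stopping at 25 mg, so no deduction is made.

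**The case against.** The best reply is that the sentence contradicts itself rather than clearly dropping a set of readings. It asks for results after every administration, in each intervention group, and that wording covers DOC after 250 mg. The table shells are still to be written (SAP section 1), and an empty PST test-dose column should expose the slip. This stands as far as it goes: the intent can be guessed and a careful programmer may get it right. But the parenthesis is the more specific instruction, it is wrong, and the shells will be built from it.

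A reader might also infer more than the documents support:

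- **That DOC reactions after 250 mg go unreported.** They do not. SAP 7.4.1 tabulates reactivity by dosage and group, the second sentence of SAP 7.5 summarises type and severity by group, and SAP 7.7 covers adverse events.
- **That a planned comparison of PST and DOC at 250 mg is lost.** The documents plan no such comparison of vital signs. The readings would not be like for like either: PST is read at 60 minutes and DOC at 30 minutes, after an earlier 25 mg.
- **That SAP 7.5 is also deficient because it sets no vital-sign categories relative to the pre-dose reading.** It never proposes the eligibility limits of protocol 6.3 as categories. Appendix C already grades reactions against baseline for systolic pressure, pulse and peak flow. Cut-points belong in the shells, which the SAP expressly defers.

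**Conclusion.** The point holds in a limited form. SAP 7.5 is wrong as written about which doses each group receives, and it contradicts both the protocol and the SAP's own introduction. Read literally, it omits one of the three real sets of post-dose readings, for at most 500 DOC subjects (five sites) or 400 (four sites) before the losses noted above, and it includes one set that cannot exist.

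The conclusion assumes that the parenthesis, rather than the broader wording before it, governs what is programmed. The effect stops at one descriptive safety table. Data collection, dosing decisions, reaction reporting, adverse events, prevalence and NPV do not change. It is most likely a drafting slip, but it sits in operative text and no other section of the SAP makes up for it.

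**What to change.** Rewrite the first sentence of SAP 7.5 so that it calls for: *vital signs after each dose (PST: 250 mg; DOC: 25 mg and 250 mg) and focused physical exam after the 250 mg dose in both groups*, summarised in frequencies and percentages by intervention group. Naming the doses in milligrams also removes any doubt about what test and full mean.

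The cost is one corrected line before the shells are drawn up. The readings are already required by protocol 6.3.1 and 6.3.2, so no new data, visits or analyses are needed.

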APPENDIX A: SCHEDULE OF EVENTS

Procedures	Enrollment Visit	Additional Visit (within 6 weeks as necessary to complete study procedures)
Written, oral, or electronic informed consent	X	
Assessment of eligibility criteria	X	
Review demographic information	X	
Administration of PCN (B-lactam) Allergy History Screening Questionnaire	X	
Review of concomitant medications	X	(X)
Allergy Validation Method 1: PST Group		
Assessment of PCN Skin Test qualification criteria	X	(X)
If additional criteria met, PCN Skin Test (prick and/or intradermal)	X	(X)
Photo documentation of skin testing (iPad)	X	(X)
Assessment of Oral Challenge qualification criteria	X	(X)
Assessment of vital signs (plus peak flow) and focused PE before and after Oral Challenge	X	(X)
If additional criteria met, Oral Challenge of 250 mg amoxicillin	X	(X)
Allergy Validation Method 2: DOC Group		
Assessment of Oral Challenge qualification criteria	X	(X)
Assessment of vital signs (plus peak flow) and focused PE before and after Oral Challenge	X	(X)
If additional criteria met, two-step Oral Challenge – initial dose of 25 mg amoxicillin followed by full dose of 250 mg	X	(X)
Completion of CRFs	X	(X)
Assessment of Adverse Events	X	(X)
Administration of subject acceptability survey	X	(X)
Provide written documentation of PCN allergy testing results or referral to allergist	X	(X)

At enrollment, all procedures will be completed unless participant cannot stay for skin testing and/or oral challenge.

(X) indicates procedures that may not have been completed during Enrollment Visit because of time constraints

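### SAP 7.5 assigns the oral-challenge dose steps to the wrong groups for its vital-sign and focused-exam summaries, so read literally it omits these results after 250 mg in the DOC group

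*SAP*

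**What the plan says.** SAP 7.5 opens: "Results of vital signs and focused physical exams (full dose only) after each administration of drug will be summarized in frequencies and percentages". The summary is to be made by group, and a parenthesis then states which doses belong to which group: "test dose for DOC group; test & full dose for PST group". The next sentence carries no dose restriction: "The type of reactions and severity will be summarized by intervention group and overall".

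The protocol describes the challenges differently.

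- **PST (6.3.1):** one administration. "After confirming the participant is qualified, amoxicillin 250 mg will be administered, and time of administration will be recorded". Section 6.2.1 also describes a single 250 mg dose after a negative skin test.
- **DOC (6.3.2):** a 25 mg preliminary dose, then a step headed "Administration of Full Challenge Dose", which is 250 mg. Appendix A has the same sequence: "initial dose of 25 mg amoxicillin followed by full dose of 250 mg".

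SAP section 1 agrees with the protocol. It describes PST as "skin testing of subjects with low-risk history followed by one-step oral challenge of subjects with negative skin tests" and DOC as "direct two-step oral challenge of subjects with low-risk history".

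**The concern.** The parenthesis in 7.5 gives two dose levels to the group that receives one, and one dose level to the group that receives two. A programmer who followed it would build a table without the DOC results after 250 mg and with a PST row that nobody can populate.

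The missing measurements matter. Under Protocol 6.3.3, a subject is told that they are not allergic when post-challenge vital signs, peak flow and focused exam are judged acceptable, and that section gives no numerical limits. The 7.5 table is where a reader could see the values behind a negative DOC result after the full dose. It is also the only summary the SAP plans for those values.

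**Working it through.** No sample-size, power or alpha figure is involved, so the check compares the two sets of group-and-dose combinations.

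**Step 1: labels.** SAP 7.5 does not define test dose or full dose. Protocol 2.2.3 uses test dose for an initial 25 mg, and Protocol 6.3.2 and Appendix A use full dose for 250 mg.

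**Step 2: cell by cell.** The protocol column comes from 6.2.1, 6.3.1, 6.3.2 and Appendix A.

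| Group and dose | Given under the protocol | Listed in SAP 7.5 |
|---|---|---|
| DOC, 25 mg (test) | yes | yes |
| DOC, 250 mg (full) | yes, if step 1 allows | **no** |
| PST, 25 mg (test) | **no** | yes |
| PST, 250 mg (full) | yes, if skin test negative | yes |

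Two cells agree. One real cell is omitted (DOC, 250 mg), and one listed cell has n = 0 by design (PST, 25 mg).

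**Step 3: focused exam.** The same sentence limits exams to the full dose. DOC is listed with the test dose only. The two conditions have no overlap in DOC, so no DOC focused exam would be summarised.

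**Step 4: would swapping the two group names repair it?** No. The text would then give test and full dose to DOC, which is right, but test dose to PST, whose only administration is the 250 mg that the protocol treats as the full dose.

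**Step 5: how many subjects.** Planned DOC enrolment is 100 per site (Protocol 4.1, SAP section 1). The Protocol Summary gives four sites and SAP section 1 gives five.

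- 100 × 4 = 400 and 100 × 5 = 500 planned DOC subjects.
- Protocol 8.2 and SAP section 6 assume that 5% have a high-risk history and do not go on to testing. Applied to DOC: 400 × 0.95 = 380 and 500 × 0.95 = 475.
- Rule-outs under Protocol 6.1.3, refusals under 6.3 and subjects who stop at step 1 reduce this further. The documents give no rates for these.

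**Step 6: what else in the SAP covers DOC after 250 mg.**

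- 7.4.1 tabulates elicited reactivity to oral challenge split by dose and group.
- The second sentence of 7.5 covers reaction type and severity by group, with no dose limit.
- 7.7 covers adverse events by group.
- 7.3 covers prevalence and NPV and does not use the 7.5 table.

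None of these summarises the vital-sign or exam measurements themselves.

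**The case against.** The strongest reply is that this is a slip of the pen with little consequence. Much of that stands. The opening of the sentence promises results after every administration in each group, and that wording would include DOC at 250 mg. The exam restriction also makes sense only for a group with two doses, which is DOC. So the sentence contradicts itself, and a deliberate omission is unlikely. Table shells are still to be written, and someone may notice the empty PST row then. But the pre-specified text is what shells are built from, and it is wrong as it stands.

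Could the mismatch come from the SAP having been written against protocol version 2.0? SAP section 1 rules that out, since it already describes PST as one-step and DOC as two-step. Could the first word of the PST entry mean the skin test? That would remove the empty PST cell. However, skin-test results have their own section (7.6), and DOC would still lack its full dose.

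A reader might also infer that the SAP loses all evidence of how DOC subjects tolerate the full dose. The documents do not support this. The parenthesis governs vital signs and focused exams only, and the outputs in step 6 remain. Protocol 6.3.3 and 7.1.3 also have reactions graded with the Appendix C table, which includes pulse change, fall in systolic pressure and peak flow relative to baseline. Abnormal values recorded as reactions therefore reach the reaction tables. What would be lost is the descriptive summary of the measurements, including those judged acceptable.

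**Conclusion.** The point holds, limited to the vital-sign and focused-exam summaries. SAP 7.5 contradicts Protocol 6.2.1, 6.3.1, 6.3.2 and Appendix A, and it contradicts SAP section 1. Read literally, it omits the DOC vital signs after 250 mg and every DOC focused exam, and it tabulates a PST dose that is not given.

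The figure of 400 to 500 is planned DOC enrolment and so an upper limit. It should not be read as the number who will receive both doses. The narrower 380 to 475 rests on applying the plan's 5% high-risk assumption to DOC.

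Data collection, sample size, reaction and adverse-event tables and the primary prevalence and NPV estimates do not change. One descriptive table is mis-specified and the underlying data would still exist, so the severity is minor to moderate. It should be corrected before the shells are built.

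**What to change.** Reword SAP 7.5 to follow the administrations in the protocol:

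- **DOC:** vital signs, including peak flow, after the test dose (25 mg) and after the full dose (250 mg).
- **PST:** vital signs, including peak flow, after the full dose (250 mg) only.
- **Both groups:** focused exam after the full dose, which keeps the SAP's existing restriction.

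Build the future table shells from that wording. If the two groups' 250 mg results are shown side by side, label the row with the observation times in Protocol 6.3.1 and 6.3.2 (60 minutes for PST, 30 minutes for DOC), because the readings are not taken at the same interval.

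In the same edit, reconcile two protocol passages. Appendix E lists a physical assessment 30 minutes after the 25 mg step, whereas 6.3.2 lists only vital signs with peak flow at that point. The exam line in 7.5 should follow whatever is settled.

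The cost is one line of SAP text, the matching shell and one reconciliation. No new data are needed.

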7.6 Analysis of Skin Testing Results

Results of skin prick testing and intradermal testing after each control and each reagent will be summarized in frequencies and percentages for those in PST group. If any result is found positive-equivocal, the size of the wheal will be summarized in means, standard deviations, medians, minima and maxima.

7.7 Analysis of Adverse Events

The Treated population and the Per Protocol population will be used for adverse event (AE) analysis. AEs will be summarized by time of onset (within/over 24 hours of study drug/test administration), relatedness to the intervention group, seriousness, severity, whether treated, outcome, and duration by intervention group, study site and overall. Categorical variables, and

continuous variables that have been categorized at discrete levels, will be summarized by frequencies and percentages. Continuous variables will be summarized by means, standard deviations, medians, minima and maxima.

Appendix A: Figure 1. Analysis Population Flow Diagram

[figure not shown]

Figure 2. Per Protocol Population Flow Diagram
